Who will not be excluded: Veterans with mild cognitive impairment, mild to moderate alcohol and substance use disorders, suicidal ideation without acute suicidality, and anxiety and depressive disorders will not be excluded because of their high co-occurrence with traumatic guilt [13-17] and recent findings that individuals with mild to moderate TBI can benefit from cognitive behavioral treatments [54]. We elected to allow Veterans to continue to engage in TAU other than trauma-focused treatments, as we do not expect TrIGR to be a stand-alone treatment for disorder specific conditions. Accordingly, all participants will be encouraged to continue to receive AUD/SUD and mental health treatment as needed, including pharmacotherapy, with their current providers throughout the study. TAU in both San Diego and Providence VAMCs consists of outpatient treatment for SUDs including relapse prevention using a

cognitive behavioral model, complementary groups such as relaxation training, sleep hygiene, and smoking cessation. Additionally, Veterans may be engaged in psycho-educational groups about PTSD (e.g., PTSD 101) that do not include trauma processing. Participants will be asked not to take part in any trauma-focused treatment such as PE, CPT, or Eye Movement Desensitization and Reprocessing (EMDR) during study participation. We will carefully track all treatment received during the active treatment and follow-up phases of the study and will evaluate whether differences in TAU are roughly equivalent across treatment groups and sites. If differences across sites exist, site will be included as a fixed effect in our analyses.

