9.5.2. Randomization. [name] will prepare the randomization table prior to the start of recruitment for each site. Randomization will be conducted separately at each site. We will use a permuted block randomization system, in which treatment assignment order is random within each block, with an equal number of participants assigned to each treatment. Block sizes will vary in random sequence between 2 and 4. We will stratify randomization by gender. We will evaluate successful randomization of other factors, such as symptom and substance use severity and demographics, and control for these factors if needed as described in section 9.11.2.

9.5.3. Feasibility of recruitment. VASDHS will serve as one of the two recruitment sites for the proposed research. We expect that three clinics within mental health services from which we will recruit heavily will be the PTSD treatment program, the Substance Abuse Mental Illness (SAMI) program, and the MST clinic. The PTSD clinic (which [name] formerly directed) completes over 50 new intakes with OEF/OIF/OND Veterans each month. During Q4 of FY2014, 540 OEF/OIF/OND Veterans with a PTSD diagnosis were seen for mental health services (either three or more sessions of psychotherapy or one medication appointment). The SAMI program has 34 OEF/OIF/OND Veterans enrolled in in the past three months. The program completes approximately 8 new intakes with OEF/OIF/OND Veterans each month. The MST Clinic sees approximately 18 new Veterans and 60 ongoing Veterans per month who are OEF/OIF/OND. We will have access to eligible participants based on the relationships and approvals we have already secured as part of Drs. [name] and [name]’s ongoing research programs and through their roles in the PTSD and substance use treatment programs at the San Diego VA. [name] current VA-

funded RCT is recruiting a similar population (although not limited to OEF/OIF/OND Veterans) and has been recruiting an average of 4-5 Veterans per month, 42% of whom (n = 33) are OEF/OIF/OND. Recruitment in the current RCT will be coming to completion as recruitment for the proposed study would be beginning, thus we will continue to receive a steady flow of referrals to our program of research.

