9.11.1. Statistical Analyses. In the initial 3-6 months, data management procedures will be developed and put into practice. Data will be entered as it is collected and quality assurance checks conducted on an on-going basis (e.g., double entry and cross validation). Data analysis will be performed in multiple stages. In the initial stage, analyses will be conducted on an on-going basis to assure strict adherence to important issues for clinical trials, such as treatment fidelity, therapeutic alliance, and therapist effects. Next, preliminary analyses will be performed by examination of the distribution of variables to assess their characteristics (means, standard deviations, and skewness). Descriptive statistics and graphs will be used to summarize the characteristics of the study population. Continuous measures will be tested for normality and homogeneity of variance. Non-normally distributed variables will be transformed to meet the normal distribution assumption for linear models. Randomization will be assessed by performing a series of Wilcoxon-rank sum tests, ² or Fisher's exact tests to compare the groups on demographic and initial baseline clinical variables. Any variables on which the groups differ initially will be explored as covariates in subsequent analyses, as described in detail for each hypothesis, and we will take this into account in the interpretation of the outcome.

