Data will be analyzed from all randomized subjects on whom we have a baseline assessment and at least one post-baseline evaluation. Responses at baseline through 6 months follow-up will be nested within subjects. Slope (change in outcome over time) will be entered into the model as a random factor and interacted with treatment group. Intercept and slope will be modeled as random effects nested within subject, and treatment group will be a fixed effect. If it is needed based on analyses in stage one, baseline covariates (e.g., demographics) will also be entered as fixed effects. Site and the Treatment by Site interaction will be included as “nuisance parameters;” that is, they must be included to account for possible overall site effects (Site) or possible site differences in treatment effects (Treatments X Site). With the balanced design (equal numbers at each site in each group), ignoring these would not increase the probability of Type I error, but it would increase the Error Sum of Squares, thus increasing the probability of Type II Error. The main effect of treatment represents the common effect size across sites if there is one, or the average site effect, if there is heterogeneity across sites. This is true because sample sizes will be balanced across treatment groups and sites. In any case, the analysis procedures will include site and site interaction effects to avoid allowing site effects to bias treatment comparisons. However, if we detect any imbalances between the treatment groups within each site, we will follow the primary analyses above with subsequent analyses considering the imbalances to verify that the conclusions are not affected by the imbalances.

Hypothesis 2: Veterans in TrIGR, compared to Veterans in SCT, will have significantly greater reduction in distress (BSI-18), shame (ISS), and significantly more improved in their quality of life (WHO-QOL-BREF) at the end of treatment and at follow up periods. This hypothesis will be analyzed using a method similar to that for testing hypothesis 1.

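### Gender is a randomisation stratum but not a prespecified term in the Hypothesis 1 model, and the rule that could admit it will practically never be triggered by arm imbalance

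*Combined protocol and SAP*

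**What the plan says.** **Randomisation (Section 9.5.2).** Two features define the strata: "Randomization will be conducted separately at each site" and "We will stratify randomization by gender". Within strata the plan uses permuted blocks, "with an equal number of participants assigned to each treatment", and "Block sizes will vary in random sequence between 2 and 4". The next rule concerns only the remaining variables: "We will evaluate successful randomization of other factors, such as symptom and substance use severity and demographics, and control for these factors if needed". The section does not say how gender is to be analysed.

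**Primary model (Section 9.11.2, Hypothesis 1).** The model has treatment, time and their interaction, with random intercept and slope within subject. Site and treatment-by-site are included in all circumstances. For anything else measured at baseline: "If it is needed based on analyses in stage one, baseline covariates (e.g., demographics) will also be entered as fixed effects". Hypothesis 2 is to be analysed in a similar way.

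**Stage one (Section 9.11.1).** The arms are compared on demographic and baseline clinical variables, and "Any variables on which the groups differ initially will be explored as covariates in subsequent analyses". The same section has a second route: drop-outs are compared with completers at baseline, and a variable on which they differ systematically may be added as a covariate.

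**Gender elsewhere.** Section 9.8.1 lists it among possible mediators and moderators. Section 9.5.6 plans to look at effect sizes in women relative to men.

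**Site elsewhere.** Section 9.4, when discussing treatment as usual, says: "If differences across sites exist, site will be included as a fixed effect in our analyses".

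**The concern.** A factor used to constrain the allocation should normally be in the analysis. If it is left out and it predicts outcome, the model-based standard error ignores the balance that the stratification bought, and the test becomes conservative.

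Here the rule for admitting covariates works against the stratification. A variable earns its place by being unbalanced between arms, and gender has been made balanced by design. The plan treats the other randomisation factor differently. Section 9.11.2 keeps site in the model because leaving it out, though harmless to Type I error, would enlarge the error variance and so raise Type II error. The same argument applies to gender, and the plan does not make it there.

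At stake are a modest amount of precision and an unambiguous primary model. Bias is not at stake.

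**Working it through.** The plan gives no figure on this point, so there is none to reproduce. Its power statement does not mention gender and is not used here.

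**Inputs from the documents.** 150 participants, 75 per site, 1:1 allocation; two sites by two genders, so four strata; four assessments; correlations between repeated measures of 0.2, 0.5 and 0.8, and attrition up to 20% (power analysis); women 11% to 60% by clinic and 11% in earlier studies (Section 9.5.6).

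**Assumed, because the documents are silent.** 11–30% women in the trial; a gender effect b of 0.3–0.5 SD; equally spaced assessments; compound symmetry with unit variance.

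**Step 1: can the balance trigger fire?** Equal numbers per arm within a block means block sizes of 2 or 4. The largest imbalance in a stratum is 2 (a block of 4 cut off after two like assignments). Women occupy two strata, so the arms differ by at most 4 women. With 16 women (11% of 150), the extreme split is 10 v 6, with men 65 v 69 in the opposite direction. Fisher's exact test gives p = 0.43 and chi-square gives p = 0.29. In 3,000 simulated allocations at each of 11%, 24% and 40% women, the chi-square test reached p < 0.05 in none; the smallest p was 0.24.

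**Step 2: variance due to gender.** v = p(1 − p)b².
- Smallest: 0.11 × 0.89 × 0.3² = 0.0088.
- Largest: 0.30 × 0.70 × 0.5² = 0.0525.

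**Step 3: a constant gender shift and the treatment-by-time contrast.** The shift is the same at every visit, so it falls into the random intercept and cancels from within-person change. With complete data the ratio of standard errors (gender omitted / included) is 1.000. A generalised least squares calculation with 20% monotone drop-out gives at most 1.002.

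**Step 4: a constant shift and a time-averaged treatment effect.** The per-person variance of the mean of four visits is (1 + 3ρ)/4, which is 0.40 at ρ = 0.2 and 0.85 at ρ = 0.8. The ratio is √(1 + v / [(1 + 3ρ)/4]).
- Smallest: √(1 + 0.0088/0.85) = 1.005.
- Largest: √(1 + 0.0525/0.40) = 1.064.

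**Step 5: a gender difference in change and the treatment-by-time contrast.** Let women and men differ by b in change from baseline to last visit. With time coded 0, 1/3, 2/3, 1, the sum of squares about the mean is 5/9. The per-person slope variance is (1 − ρ)/(5/9), which is 1.44 at ρ = 0.2 and 0.36 at ρ = 0.8. The ratio is √(1 + v / slope variance).
- Smallest: √(1 + 0.0088/1.44) = 1.003.
- Largest: √(1 + 0.0525/0.36) = 1.070.

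Any further between-person slope variation enlarges the denominator and shrinks this inflation. A gender main effect alone does not remove it; gender-by-time does.

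**Step 6: effect on the test.** Balance leaves the true sampling error unchanged, so a standard error too large by a factor k gives an actual two-sided level of 2[1 − Φ(1.96k)]. For k = 1.003 this is 0.049; for k = 1.070 it is 0.036.

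**The case against.** The strongest reply is that a reader might infer a loss in the primary test from the usual two-group formula. For a single visit, √(1 + v) gives √1.0088 = 1.004 to √1.0525 = 1.026, or 0.4–2.6%. That is the wrong model for Hypothesis 1, which concerns reductions and is tested through slope by treatment with random subject effects. Step 3 shows that a constant gender shift then costs essentially nothing, and that adding only a gender main effect would recover essentially nothing. This part of the objection stands. What remains is the time-averaged treatment effect, which Section 9.11.2 also interprets when it discusses site, and the case where gender affects change.

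A reader might also infer that gender is barred from the model. The documents do not say that. Section 9.11.2 sets no p-value for need, and the drop-out comparison in Section 9.11.1 could bring gender in regardless of arm balance. But whether a randomisation factor is in the primary model then depends on decisions made after data are seen, which prespecification would avoid.

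It is fair, too, that no passage shows gender to predict guilt severity. Clinics differ in their share of women, but the step from there to a gender effect on guilt is conjecture. The effect sizes above are therefore assumptions.

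Finally, the two site sentences might be read as leaving the role of site open. Section 9.4 speaks in the context of treatment as usual, and Section 9.11.2 settles the matter for the primary model. The mismatch is one of wording.

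**Conclusion.** The point holds as a low-severity gap in prespecification. Gender constrains the allocation, is not a fixed term in the Hypothesis 1 or 2 models, and will practically never qualify through arm imbalance; it will normally be omitted unless the drop-out route brings it in.

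The treatment estimate is unbiased either way, and any error in the test is in the conservative direction. Under the stated assumptions, the inflation of the standard error is:

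| Assumed gender effect (0.3–0.5 SD) | Contrast | Inflation |
|---|---|---|
| Constant shift | Treatment-by-time | 0–0.2% |
| Constant shift | Time-averaged treatment effect | about 0.5–6% |
| Difference in change by last visit | Treatment-by-time | about 0.3–7% |

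The upper ends need 30% women and a 0.5 SD effect, together with the least favourable correlation for that contrast (0.2 for the second row, 0.8 for the third). If gender does not predict guilt or its change, nothing is lost. The documents do not support a claim of bias, or of a material loss of power from a constant gender difference in guilt.

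**What to change.** In Section 9.11.2, state that gender and gender-by-time are fixed effects, alongside the site terms already there, in every Hypothesis 1 and Hypothesis 2 model, whatever the stage-one comparisons show. Keep the stage-one rule for other variables only. In Section 9.4, reword the conditional sentence on site so that it agrees with Section 9.11.2.

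The cost is a few sentences and a few degrees of freedom: one for gender, plus one for gender-by-time if time is linear or three if the four assessments are categorical. No new data are needed, because gender must be known at randomisation.

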9.7. Treatment Conditions

9.7.1. Experimental condition – TrIGR.

TrIGR will be administered during six 90-minute individual sessions. **Module 1** (delivered over 2 sessions) includes an overview of common reactions to trauma and provides psycho-education regarding posttraumatic guilt and shame. We review the NAG model and then review common sources of deployment-related traumatic guilt and shame [58, 59], such as taking part in or witnessing atrocities, failing to perform a duty, failing to stop a sexual assault, or enjoying or feeling nothing when killing.

Module 2 (delivered over 2 sessions) uses cognitive restructuring to help patients evaluate the four types of cognitive errors contributing to posttraumatic guilt identified in prior research [60]. Many Veterans have more than one trauma over which they experience guilt. Two sessions of Module 2 gives us adequate time to review up to three traumatic events. To identify cognitions that are associated with guilt (e.g., “I should have...” or “I shouldn’t have...”), the therapist conducts a detailed review of the traumatic event(s) with the patient. This detailed review is needed because what may initially appear to be the source of guilt (e.g., “I killed someone”) may turn out be a more nuanced cognition upon further exploration (e.g., “I was justified in killing the insurgent, but I shouldn’t have enjoyed it”). Each of the four cognitive errors is reviewed; however, the amount of time dedicated to each is tailored to the patient’s needs and experiences.

In reviewing hindsight bias, a patient may express beliefs that “I knew the combatant wasn’t a threat, but I shot anyway.” The therapist leads the patient through several exercises to normalize how common it is to come to believe after the fact that someone had information that they did not actually have until later. Therapists then explore with patients what they actually knew at the time versus what they came to believe they knew after the fact given the negative outcome.

In the justification analysis, the therapist and patient explore what choices were truly available at the time of the trauma as people frequently believe after the fact that there must have been a way for a better outcome to have occurred. Patients write down all of the choices available to them during the event (e.g., shooting the person who is suspected to be strapped with a bomb who is ignoring orders to not come any closer, not shooting) and the potential pros and cons of each option. This examination generally leads to the realization that there were no “good” options, all options would have led to some undesirable outcome that could also contribute to regret, that an idealized option did not exist at the time, or that the option taken was either the best of the available options in some way or no worse than the other available options.

In the responsibility analysis, the patient initially rates his/her perception of responsibility for what happened on a 0-100% scale. The therapist then leads the patient through an exercise to demonstrate that there are multiple factors responsible for all outcomes. The patient and therapist brainstorm together to identify all of the other factors that contributed to the traumatic event (e.g., orders, rules of engagement, how much sleep the patient had had in the days leading up to the event, etc.) and the percent to which the patient feels each was responsible. Patients are then able to view their self-assigned level of responsibility relative to the total of these other factors.

Finally, in the wrongdoing analysis, the difference between intentionally setting out to do harm and an unfolding bad outcome is discussed. This discussion is generally straightforward for many deployment traumas where Veterans can acknowledge that they did not intend to cause harm (e.g., switching patrols with someone who ended up getting killed). However, this discussion may be more complicated with a Veteran who hurt or killed others outside of the rules of engagement. In such cases, helping the Veteran

consider the context of war, emotions that were at play such as anger and grief, the extent of the Veteran's guilt/remorse now and how much he or she has suffered since the event, or if the person intends to do anything similar again, can help give context to the concept of wrongdoing. The goal is not to lead someone to believe that the trauma "was not his fault" but rather to help put the traumatic event and actions/choices into context to help the patient move toward a more positive life marked by less suffering and impairment.

Module 2 ends with a discussion of the function that guilt and shame have served in the patient's life (e.g., "It keeps me from hurting more people") and what it might mean to feel less guilt/shame. This discussion allows the therapist and patient to transition to **Modules 3 and 4** (1 session each) where the focus is on identifying the patient's values and setting goals to live a more value-driven life. The point is made that certain values must be very important to the patient since violating a value during the trauma has caused a great deal of suffering since. Patients cannot undo the past, but can take action to live a more value-driven life going forward. Positive ways to express values rather than through guilt and shame are discussed with an aim of setting goals toward value driven growth. [name] and colleagues describes the protocol in more detail [43].

9.7.2. Comparison Condition – Supportive Care Therapy (SCT). Supportive Care Therapy (SCT) is a non-directive therapy and quite distinct from TrIGR both theoretically and in practice. SCT applies Rogerian principles of unconditional positive regard, genuineness, and empathic understanding in session and emphasizes the therapeutic relationship as the mechanism that enhances well-being and facilitates healing. SCT therapy will employ specific techniques to convey a deep understanding of emotions, thoughts, and behaviors of the Veterans receiving this treatment. Specific techniques include content-focused paraphrasing, exploration through open-ended questions (with a goal of empathic understanding), and emotion-focused reflection and validation. At the end of each session, therapists will offer an integrative summary of the session's content and process.

SCT will be offered in six 90-minute sessions in order to parallel the dose of TrIGR. Because this is a client-centered therapy, Veterans will be free to choose the content of each session. If Veterans elect to discuss their trauma experience, this will be allowed and therapists will respond to this content as they would any other content area – with an open, nonjudgmental stance and unconditional positive regard. Consistent with the SCT model, therapists will be explicitly instructed not to provide advice, assign activities, or suggest strategies and techniques employed in TrIGR or any other evidenced-based intervention (e.g., in vivo exposures). Otherwise, there are few guidelines in terms of the structure and content in SCT. The first few sessions will emphasize rapport building and the remaining sessions will have an increasing focus upon a review of the process of the therapy as a whole and the relationships that were formed between the therapist and Veteran.

The SCT condition has been used in previous psychosocial intervention studies, and the PI and her collaborators have utilized SCT in other RCT's with OEF/OIF/OND Veterans (e.g., NCT01009112). Dropout in our past trial did not differ between SCT and other conditions. The rationale for using SCT as a comparison condition is to provide a credible therapeutic alternative to control for nonspecific therapeutic factors [61, 62]. In addition to controlling for passage of time, testing, and statistical regression toward the mean, this non-specific comparison condition will control for the nonspecific aspects of therapy that characterize most forms of therapy and are distinct from the hypothesized active mechanisms of TrIGR.

Selection of control groups for psychosocial treatments is complex. Unlike in medication trials, it is not possible to create a placebo treatment that controls for all aspects of the treatment delivery except the active mechanism(s). A variety of control conditions have been used in behavioral treatment research, but the optimal control depends on the stage of research. For early Stage II trials [63, 64] such as the proposed study, non-specific comparison designs have been recommended [e.g., 62]. [name], who has extensive experience delivering and supervising non-specific therapies across multiple trials ([e.g., 62], NCT02157779), will train and supervise the therapists on SCT (see below). The manual can be found in Appendix 12e.

9.7.3. Therapist Training. Two therapists will be hired for ten hours per week each at each site (four therapists in total). All therapists will deliver both therapies with careful ongoing fidelity assessment to monitor for cross-over effects. We considered hiring one therapist for twenty hours per site but decided on

two per site to be better able to control for therapist effects. The team of investigators will train study therapists on both TrIGR and SCT using audio recordings, role plays, and evaluating fidelity on at least two patients, and will hold weekly ongoing supervision sessions. Therapists will first receive didactic training in both protocols, including a review of the research on guilt related to trauma, featuring demonstrations and role-plays of specific components of each intervention. Therapists will treat at least two patients to fidelity with each protocol (see 9.7.4) before treating a study patient. Therapists will be carefully supervised using audio recordings of therapy sessions. Weekly clinical supervision will be provided by [name] for TrIGR and [name] for SCT and will examine clinical issues and adherence to the study protocol. [name] and [name] developed TrIGR, [name] has conducted research with TrIGR, and [name] has delivered and supervised supportive non-specific therapy protocols in several large trials [e.g., 62] including her current research (NCT02157779).

9.7.4. Treatment Fidelity. Our approach to treatment fidelity and adherence utilizes accepted standards [65] including: (1) treatment manuals with weekly objectives, outcomes, and agendas, (2) therapist training (to avoid bias, therapists will be trained for both interventions), and (3) ongoing evaluation of treatment fidelity through audio-rating of therapy sessions and supervision. To identify problems early, [name] will listen to audio-recordings of each therapist once per week for a period of 6 weeks post-training and complete fidelity rating sheets for each session (see Appendix 12f-g). Corrective feedback will be provided as needed. Thereafter, [name] (who is trained to fidelity and experienced in delivering and rating fidelity for both TrIGR and SCT) will rate 10% of remaining audio-recorded sessions at random as determined by the study statistician, [name]. Further, Drs. [name] (for TrIGR) and [name] (for SCT) will have weekly supervision of therapists to evaluate their implementation of and adherence to the therapy manuals. The participant evaluation method of quality assurance involves asking each participant to complete a brief checklist that queries the content of the session (e.g., “Did the therapist discuss the relationship between guilt and trauma?”). This method provides estimates of inter-rater reliability. We will maintain inter-rater reliability at $\boxed{?} = .90$. In addition, therapists will keep a session-by-session “TrIGR Session Tracking Form” and “SCT Session Tracking Form” which includes self-ratings about the “% of time” of each session was spent “using the manual” and covering the relevant module content.

9.7.5. Standard Pharmacotherapy. In regard to pharmacotherapy, the VA follows treatment guidelines that require standardized prescribing practices for individuals with PTSD, depression, and AUD. We expect at least 85% of participants will be receiving medications based on these guidelines. We recognize that pharmacotherapy and changes in medications will be an uncontrolled source of variance but expect that any changes will be similar across treatment conditions and thus balanced by randomization. We considered recruiting participants who were not on medication or asking participants to be medication stable prior to study entry. However, psychotropic medications have well documented effectiveness for the treatment of PTSD, anxiety and depression and withholding such medication would be inappropriate for this high-risk population. Study coordinators will record from VA medical records and patient self-report all treatment (psychotherapy and medication) in which Veterans participate in the VA. Participants will also be asked about any treatment outside of the VA. We will compare treatment as usual between our two conditions and, if differences in any variables are found, include these as covariates in our analyses.

9.7.6. If Participants’ Alcohol/Substance Use Worsens During Treatment. If a therapist or assessor identifies worsening alcohol or substance use, the investigators will evaluate whether best clinical care indicates a need for more intensive SUD treatment. PIs will be contacted if a participant reports increased or risky substance use. If more intensive treatment is needed for any reason, we will assist in establishing treatment, then discontinue study participation following a final evaluation. Please see the Human Subjects section for the plan to address clinical worsening during study participation, including if participants display safety concerns such as suicidality or risk of violence.

